8.5 Discontinuation

A subject may withdraw from trial or from treatment at any time (prior to first dose or during treatment period) at his/her own request. A subject may be withdrawn at any time at the discretion of the investigator. Discontinued subjects will not be replaced.

Medical reasons for permanent discontinuation of IMP are given in Section 9.8.1.

Assessments

Subjects who permanently discontinue IMP for any reason will be asked to attend an early termination visit and return to the trial site for 1 or 2 additional visits as indicated below depending on the time of discontinuation of IMP (see the SoP [Section 4] for data to be collected at these visits). The investigator will review any AEs which will be followed-up according to Section 11.6, if the subject agrees.

Subjects who permanently discontinue IMP prior to Week 16 will be asked to attend:

- Early termination visit.
- Nominal Week 16 visit (16 weeks after randomisation).
- Safety follow-up visit (16 weeks after last administration of IMP).

Subjects who permanently discontinue IMP at Week 16 or after Week 16 will be asked to attend:

- Early termination visit.
- Safety follow-up visit (16 weeks after last administration of IMP).

If a subject withdraws from the trial, he/she may request destruction of any samples taken and not tested, and the investigator must document this in the site's trial records.

Reason(s) for discontinuation from IMP and withdrawal from the trial must be recorded in the medical records and the eCRF (lack of efficacy, AE, withdrawal by subject, lost to follow-up, death, other). For subjects randomised to IMP but not attending any post-baseline visits, it will be recorded whether any safety evaluations were performed after exposure to IMP.

Lost to follow-up

A subject will be considered lost to follow-up if they repeatedly fail to return for scheduled visits and if the trial site is not able to get in contact with the subject.

The following actions must be taken if a subject fails to return to the trial site for a required visit:

- The trial site must attempt to contact the subject and reschedule the missed visit as soon as possible and counsel the subject on the importance of maintaining the assigned visit schedule and ascertain whether or not the subject wishes to and/or should continue in the trial.

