11.2 Reporting of adverse events

AEs reported by the subject or observed by the investigator must be recorded on the AE form of the CRF and should be described in the following manner:

The *AE term* must be in precise English medical terminology (i.e. not necessarily the exact words used by the subject). Whenever possible, a specific diagnosis should be stated (for example 'allergic contact dermatitis').

The *duration* of the AE must be reported by the start date and stop date of the event. In addition, it must be recorded whether the AE started prior to start of IMP.

AEs must be classified in terms of severity, causality and outcome according to the definitions in Appendix 3.

Action taken with trial treatment: Any action taken with IMP as a consequence of the AE must be recorded (dose not changed, dose reduced, dose increased, drug interrupted, drug withdrawn, not applicable, unknown).

Trial ID: LP0162-1325	Date: 14-Aug-2018	Version: 4.0
		Page 85 of 169

Other action taken: any other action taken as a result of the AE must be recorded (none, concomitant medication, concomitant procedure).

Withdrawn due to AE: it must be recorded whether the AE leads to withdrawal from the trial.

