12.3 Statistical analysis

12.3.1 Disposition of subjects

Subject disposition will be presented separately for subjects in initial treatment, in maintenance treatment, and in open-label treatment. For all randomised subjects the reasons for permanent discontinuation of IMP and for leaving the trial in the initial treatment period will be presented by last visit attended and by treatment group. For the subjects in the maintenance safety analysis set, the reasons for permanent discontinuation of IMP and for leaving the trial or treatment arm will be presented by last visit attended and by treatment group at Week 16. For the subjects in the open-label safety analysis set, the reasons for permanent discontinuation of IMP and for leaving the trial or treatment arm will be presented by last visit attended and by the assigned treatment group at Week 16. For the subjects in the open-label safety analysis set, the reasons for permanent discontinuation of IMP and for leaving the trial will be presented by last visit attended.

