12.3.7.1 Adverse events

AEs will be coded during the course of the trial according to Medical Dictionary for Regulatory Activities (MedDRA). AEs will be presented by preferred terms and primary system organ class (SOC).

Treatment-emergent AEs will be summarised, however, all AEs recorded during the course of the trial will be included in the subject data listings. An event will be considered treatment-emergent if started after the first use of IMP or if started before the first use of IMP (applicable if subject had a wash-out) and worsened in severity thereafter. The tabulations described in the following will only include the treatment-emergent events. In each of the tabulations, AEs will be defined by MedDRA preferred terms within primary SOC.

An overall summary of the number of treatment-emergent AEs, number (percentage) of subjects with any treatment-emergent AEs, SAEs, deaths, premature discontinuations from the trial due to AEs, treatment-related AEs and severe AEs will be presented.

The number of AEs and the number of subjects experiencing each type of AE will be tabulated by treatment group. The percentage of subjects with AEs in the initial treatment period will be compared between treatment groups by a chi-square test or Fisher's exact test (if expected cell count < 5).

The severity for each type of AE will be tabulated by treatment group.

The causal relationship to IMP for each type of AE will be tabulated by treatment group.

Related AEs are defined as AEs for which the investigator has not described the causal relationship to IMP as 'not related'. The number of related AEs and the number of subjects experiencing each type of related AE will be tabulated. The percentage of subjects with related AEs in the initial treatment period will be compared between treatment groups by a chi-square test or Fisher's exact test (if expected cell count <5).

SAEs and AESIs will be evaluated separately. A narrative for each SAE will be given. AESIs and AEs leading to withdrawal from trial will be tabulated and listed.

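### The AE outputs are defined by leaving the trial, so AEs that ended treatment in subjects who stay for follow-up can be missing from the SOC/preferred-term table

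*Protocol*

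**What the plan says.** Protocol Section 12.3.7.1 has two outputs on AEs that cut participation short, and both are worded in terms of the trial. In the overall summary, the list includes "SAEs, deaths, premature discontinuations from the trial due to AEs, treatment-related AEs and severe AEs will be presented". Among the tables and listings, "AESIs and AEs leading to withdrawal from trial will be tabulated and listed". Neither this section nor SAP Section 6.7.1 specifies an output for AEs that led to permanent discontinuation of IMP. SAP 6.7.1 covers assignment of AEs to periods and the sort order of tables, and otherwise says only that AEs are summarised and listed.

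Elsewhere the protocol treats the two events as distinct:

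- Section 8.5: "A subject may withdraw from trial or from treatment at any time". It adds: "Subjects who permanently discontinue IMP for any reason will be asked to attend an early termination visit and return to the trial site for 1" (the sentence goes on; the number of further visits, one or two, depends on when IMP was stopped).
- Section 9.8.1 lists AE-type reasons for permanently stopping IMP. It does not say that these subjects leave the trial.
- Section 11.2 gives the AE form two items. One is the action on IMP: "Any action taken with IMP as a consequence of the AE must be recorded", with drug withdrawn as one of the options. The other is trial withdrawal: "it must be recorded whether the AE leads to withdrawal from the trial".
- Section 12.3.1 covers both events at subject level: "For all randomised subjects the reasons for permanent discontinuation of IMP and for leaving the trial in the initial treatment period will be presented". The breakdown there is by treatment group and by the last visit each subject attended. AE is one of the reasons recorded under Section 8.5.

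**The concern.** AEs that end treatment are a central tolerability result. They are also where the protocol's own IMP stopping rules show up in the data. A reader of the report will look for them in the table of AEs leading to discontinuation, broken down by SOC and preferred term and compared by eye across arms.

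As specified, that table is keyed to leaving the trial. A subject whose IMP is stopped for an AE, and who then attends the visits Section 8.5 asks for, need not be recorded as having left. The better sites follow Section 8.5, the fewer treatment-ending AEs this table may contain. If retention after stopping IMP differs between arms, the arms are also affected unequally. The design relies on such retention: the primary analysis of the primary endpoints (Section 12.3.5.1.1) uses Week 16 data from subjects who stopped IMP earlier.

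**Working it through.** The documents give no figure for this category, so there is nothing to reproduce. The check is a comparison of text, followed by an illustration.

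**Step 1: what triggers each output.**

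| Source | Event used | Level of detail |
|---|---|---|
| 12.3.7.1, overall summary row | leaving the trial because of an AE | subjects |
| 12.3.7.1, table and listing | AE leading to leaving the trial | AE |
| 11.2, action on IMP | AE led to drug being withdrawn | AE, collected but with no output specified |
| 11.2, trial withdrawal | AE led to leaving the trial | AE, collected and matching the planned table |
| 12.3.1, disposition | reason for stopping IMP, and for leaving the trial | subjects by reason, no preferred term |
| SAP 6.7.1 | none added | not applicable |

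**Step 2: can the two events diverge?** Yes. Section 8.5: "Subjects who permanently discontinue IMP prior to Week 16 will be asked to attend" an early termination visit, a nominal Week 16 visit and a safety follow-up visit 16 weeks after the last IMP. Those who stop at or after Week 16 are asked to attend the early termination and follow-up visits only. In both cases the subject can have a drug-withdrawn AE without being marked as withdrawn from the trial.

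**Step 3: is the missing breakdown available elsewhere?** Only in part. Section 12.3.7.1 tabulates every treatment-emergent AE by type and treatment group, but does not mark which ones ended treatment. Disposition gives a head count for reason AE without saying which AEs. SAEs have narratives and AESIs have their own tabulation and listing. A non-serious AE that is not an AESI but ended treatment appears only among all AEs.

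**Step 4: size.** Let n be the arm size, d the share of the arm that stops IMP for an AE, and r the share of those not recorded as withdrawn from the trial. Then

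- true number = n × d
- number shown = n × d × (1 − r)
- relative shortfall = r

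n is 585 and 195 (Section 12.1). The documents give neither d nor r, so the values below are assumptions.

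| d | Tralokinumab, n × d | shown at r = 0.5 | Placebo, n × d | shown at r = 0.5 |
|---|---|---|---|---|
| 1% | 585 × 0.01 = 5.9 | 2.9 | 195 × 0.01 = 2.0 | 1.0 |
| 3% | 585 × 0.03 = 17.6 | 8.8 | 195 × 0.03 = 5.9 | 2.9 |
| 5% | 585 × 0.05 = 29.3 | 14.6 | 195 × 0.05 = 9.8 | 4.9 |

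At r = 0 the table is complete. At r = 1 it is empty whatever d is.

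**The case against.** The strongest reply is that withdrawal is not used consistently, so the planned table may already be meant to capture IMP stops. Three places support this:

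- Section 7.3 requires a subject to finish all trial periods to count as a completer. Someone who stops IMP at Week 6 and attends only the Section 8.5 visits is then a non-completer, and might be counted as a premature discontinuation from the trial.
- Section 12.3.5.1 defines its discontinuation event as withdrawal from either the treatment or the trial.
- SAP Section 6.6.2 identifies subjects withdrawn for an AE by their reason for stopping IMP.

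This stands as evidence of mixed usage, and it is why r could be zero. It does not settle the matter. The last two are efficacy definitions, and SAP 6.6.2 applies only to sensitivity analysis 2. Section 7.3 defines completion, not what an AE led to. Sections 8.5 and 11.2, which govern what sites record, separate the events explicitly.

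The second reply is that little is lost, and much of it stands. The events are in the main AE tables with severity and causality, and in the listings. Disposition gives the count of IMP stops for AE by treatment group for the initial and maintenance periods, and that count does not depend on retention. Malignancies, apart from the types exempted in Section 9.8.1, are AESIs. Liver values have shift tables, out-of-range listings (Section 12.3.7.3) and SAP Table 2 thresholds.

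A reader might infer that a subject stopped for anaphylaxis vanishes from the safety report. The documents do not support that: the event can be absent from this one table and its summary row, not from the AE reporting.

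**Conclusion.** The point holds as a gap in the specified AE outputs. Read as written, the table and summary row can omit AEs that ended treatment in subjects who remain in the trial, and no other planned output gives those AEs by SOC and preferred term. That conclusion rests on the text and on the ordinary reading that the table follows the trial-withdrawal field on the AE form.

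The size is unknown, from none to all such AEs. It depends on how many subjects stay and on how sites complete that field. The counts in the illustration rest wholly on assumed rates.

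Two stronger readings go too far. A reader might infer that most treatment-ending AEs will be omitted, but that follows only if high retention is assumed. A reader might also infer that a planned statistical comparison with placebo is biased. Section 12.3.7.1 plans tests for all AEs and for related AEs, and specifies none for this category, so what is affected is a descriptive by-group display. No efficacy or confirmatory result changes. It should be corrected because the distinction is already built into data collection and the remedy is simple.

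**What to change.** In Section 12.3.7.1 and SAP Section 6.7.1:

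1. Tabulate and list treatment-emergent AEs whose recorded action was drug withdrawn, labelled as AEs leading to permanent discontinuation of IMP, by SOC and preferred term, treatment group and period.
2. Add the corresponding row to the overall AE summary, and keep withdrawal from the trial because of an AE as a separate row.
3. Reconcile the number of subjects with the disposition count of IMP stops for AE, and explain differences. Some are to be expected: one subject may have several such AEs, and SAP 6.7.1 assigns AEs to periods by start date while disposition is presented by last visit attended.

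The cost is a few extra tables and some SAP wording, using a field already collected. The reported discontinuation figure may look less favourable than one based on trial withdrawal.

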12.3.7.2 Vital signs

The change in vital signs (blood pressure, heart rate, body temperature) from baseline to each visit will be summarised by visit and treatment group as mean, standard deviation, median,

Trial ID: LP0162-1325	Date: 14-Aug-2018	Version: 4.0
		Page 112 of 169

minimum and maximum values for the safety analysis set, the maintenance safety analysis set, and the open-label safety analysis set.

12.3.7.3 Clinical laboratory evaluation

The change in each of the laboratory parameters from baseline to each visit will be summarised by visit and treatment group as mean, standard deviation, median, minimum and maximum values for the safety analysis set, the maintenance safety analysis set, and the open-label safety analysis set.

Laboratory parameters will be classified as 'low', 'normal' or 'high', depending on whether the value is below, within or above the reference range, respectively. A shift table will be produced showing the categories at baseline against those at end of treatment. Subjects with laboratory parameters outside the reference range will be listed.

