5.6 Ethical considerations

No children or other vulnerable subjects incapable of giving informed consent will be enrolled in this clinical trial. Furthermore, women who are pregnant, breastfeeding, or trying to become pregnant will not be enrolled in this clinical trial. Women of child-bearing potential have to agree to use a highly effective method of contraception to prevent pregnancy during the clinical trial and until 16 weeks after discontinuation of treatment with the IMP. In addition, all female subjects of child-bearing potential will have a pregnancy test performed before, during and at End of Treatment to ensure that no foetuses are exposed to the IMP.

In this clinical trial, the efficacy of tralokinumab will be evaluated in adult subjects with moderate-to-severe AD who are otherwise healthy. Tralokinumab treatment will be compared with a placebo control group. Subjects who do not achieve a clinical response (IGA 0/1 or EASI75) at Week 16 will be transferred to open-label tralokinumab 300 mg Q2W treatment with optional use of TCS. Similarly, during the maintenance treatment period, subjects who

Trial ID: LP0162-1325	Date: 14-Aug-2018	Version: 4.0
		Page 35 of 169

meet the protocol definition of transfer to open-label will be treated with open-label tralokinumab 300 mg Q2W with optional use of TCS.

Altogether, the risks associated with participating in this clinical trial are considered very low and outweighed by the benefit of a potential future treatment option for moderate-to-severe AD. Moreover, 75% of the subjects will be randomised to active treatment with tralokinumab in the initial treatment phase and those who do not achieve a clinical response at Week 16 (including subjects randomised to placebo) will be treated with open-label tralokinumab in the maintenance phase with a potential effect and benefit for the individual subject.

In accordance with the current version of the International Council for Harmonisation (ICH) Good Clinical Practice (GCP) guidelines, qualified medical personnel employed by LEO will be readily available to advise on trial-related medical questions. Medical monitoring will be performed throughout the trial. Safety data will be reviewed regularly by Global Pharmacovigilance, LEO and an independent Data Monitoring Committee (DMC; see Appendix 4H) to ensure that prompt action is taken, if needed, to maximise patient safety.

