7.1 Overall trial design

Overview

This is a phase 3 randomised, double-blinded, placebo-controlled trial in adult subjects with moderate-to-severe AD. The trial will consist of a screening period of 2 to 6 weeks (Weeks -6/-2 to 0), an initial treatment period of 16 weeks (Weeks 0 to 16) and a maintenance treatment period of 36 weeks (Weeks 16 to 52). The primary endpoint is assessed at Week 16, and the final efficacy assessment will be conducted at Week 52. A 14-week off-treatment follow-up period for the assessment of safety is also included (Weeks 52 to 66). Subjects not achieving a clinical response at Week 16 as well as those who meet certain criteria during maintenance treatment will be transferred to open-label tralokinumab 300 mg Q2W treatment with optional use of TCS up to Week 52. An overview of the different parts of the trial is provided in Panel 1 and Panel 9.

Screening period (Week -6 to Week 0)

The screening period has a minimum duration of 2 weeks and a maximum duration of 6 weeks and includes 1 or 2 screening visits. The exact duration of the screening period depends on the washout period defined by the exclusion criteria (Section 8.3). If a washout is not required, screening will be reduced to 2 weeks and only requires 1 visit (Week -2; visit 2), i.e., the 2 screening visits will be merged. Similarly, if only a 2-week wash-out is required, screening visits 1 and 2 will be combined (Week -2; visit 2). Eligibility will be assessed at the (first) screening visit and on Day 0 prior to randomisation.

All subjects will attend a screening visit 14 days before baseline (Week -2; visit 2) where they will receive electronic diary (eDiary) training and start the eDiary. Data entered in the eDiary during the 2 weeks before randomisation will be used to calculate baseline values of the patient-reported outcomes (PROs).

All subjects will use an emollient twice daily (or more, as needed) for at least 14 days before randomisation and will continue this treatment throughout the trial. Subjects will initiate emollient treatment no later than the Week -2 visit.

Trial ID: LP0162-1325	Date: 14-Aug-2018	Version: 4.0
		Page 41 of 169

Initial treatment period (Week 0 to Week 16)

Following the screening period, approximately 780 subjects will be randomised 3:1 to one of the following groups stratified by region and disease severity (IGA of 3 or 4)

- Tralokinumab 600 mg (4 mL) at Day 0 (hereinafter "baseline"), then 300 mg (2 mL) Q2W.

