- Placebo (4 mL) at baseline, then placebo (2 mL) Q2W.

Maintenance treatment period (Week 16 to Week 52)

Subjects achieving a clinical response at Week 16 will continue into maintenance treatment that will continue until Week 52.

Clinical response is defined as IGA of 0 or 1, or at least 75% reduction in EASI score from baseline (EASI75).

Subjects randomised to tralokinumab in the initial treatment period will be re-randomised 2:2:1 to one of the following Q2W maintenance regimens stratified by region and IGA response at Week 16 (IGA 0/1 or IGA >1):

- Tralokinumab 300 mg (2 mL) ('tralokinumab Q2W').
- Alternating dose administrations tralokinumab 300 mg (2 mL) and placebo (2 mL) ('tralokinumab Q4W').
- Placebo (2 mL).

Subjects randomised to placebo in the initial treatment period who achieve a clinical response at Week 16, defined by IGA of 0 or 1, or EASI75 will continue to receive placebo Q2W in the maintenance treatment period.

Transfer to open-label treatment

Subjects will be transferred from maintenance treatment to open-label treatment (tralokinumab 300 mg Q2W with optional use of TCS) if they meet the criteria listed below. Transfer to open-label may occur at any visit while the subject is in the maintenance treatment period but no earlier than Week 22.

Subjects with IGA=0 at Week 16:

• IGA of at least 2 and not achieving EASI75 over at least a 4-week period (i.e., over 3 consecutive visits).

Subjects with IGA=1 at Week 16:

• IGA of at least 3 and not achieving EASI75 over at least a 4-week period (i.e., over 3 consecutive visits).

Subjects with IGA >1 at Week 16:

• Not achieving EASI75 over at least a 4-week period (i.e., over 3 consecutive visits).

Subjects who are transferred to open-label treatment will continue their scheduled visit sequence.

Open-label treatment (Week 16 to Week 52)

Any subject that does not achieve the protocol defined clinical response at Week 16 will be treated with open-label tralokinumab 300 mg Q2W with optional use of TCS. The open-label treatment will extend to Week 52.

For selected countries

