# 5 Trial Analysis Sets

The trial analysis sets are defined in the protocol and the following modifications to the analysis sets for the initial- and maintenance periods are introduced.

All subjects randomised to initial treatment who were exposed to IMP are included in the full analysis set (FAS) and will be analysed for efficacy up to Week 16 (visit 12). For subjects not exposed to IMP, the decision to withdraw can't be biased by knowledge of the assigned treatment due to the blinding. This definition of the FAS implements the consideration mentioned in the protocol regarding special excluded cases with reference to ICH E9, Section 5.2.1.

The safety analysis set comprises all subjects randomised to initial treatment who were exposed to IMP. The protocol further specifies to exclude subjects from the safety analysis set for whom no post-baseline safety data are available. However, since all subjects receive the first dose of IMP in connection with the Week 0 visit and are subsequently monitored for immediate drug reactions, all exposed subjects are considered to have post-baseline safety data available and no such further exclusions will be made.

The maintenance analysis set is defined in the protocol as all subjects who receive tralokinumab in the initial treatment period and who are re-randomised to maintenance treatment. In addition to this, subjects who are not exposed to maintenance treatment will be excluded from the maintenance analysis set. This follows the same principle that leads to exclusion of unexposed subjects from the full analysis set and is in alignment with ICH E9.

The maintenance safety analysis set comprises all subjects who are re-randomised and receive at least one dose of maintenance treatment.

The open-label safety analysis set comprises all subjects who at any point in time enter the open-label treatment arm and receive at least one dose of open-label treatment.

For the follow-up period the safety follow-up analysis set will be used as the basis for evaluation of adverse events during the follow-up period. It comprises all subjects for whom date of last contact is after the date of exposure end, where exposure end is defined as the Week 52 visit (Week 68 visit for subjects enrolled in short-term extension) for subjects

Trial ID: LP0162-1325	Date: 20-May-2019	Version: 1.0
		Page 10 of 31

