## 6.8 General Principles

#### 6.8.1 Baseline value

Unless otherwise specified, the baseline value is defined as the latest pre-dose assessment.

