## 6.8.8 Treatment Labels

Period	Label Used in Text	Label Used in Tables	Order in Table
Initial period	Tralokinumab Q2W	Tralokinumab Q2W	1
Initial period	Placebo	Placebo	2
Maintenance	Week 16 Tralokinumab responders:	Week 16 Tralokinumab responders:	1
period	Tralokinumab Q2W	Tralokinumab Q2W	
Maintenance	Week 16 Tralokinumab responders:	Week 16 Tralokinumab responders:	2
period	Tralokinumab Q4W	Tralokinumab Q4W	
Maintenance	Week 16 Tralokinumab responders:	Week 16 Tralokinumab responders:	3
period	Placebo	Placebo	
Maintenance	Week 16 Placebo responders:	Week 16 Placebo responders:	4
period	Placebo	Placebo	
Open-label period	Tralokinumab Q2W + optional TCS	Tralokinumab Q2W + optional TCS	1

Table 6: Treatment labels for the clinical trial report text and tables

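### Open-label laboratory and vital-sign changes are taken from Day 0, so for subjects who started on placebo they include at least 16 weeks before any tralokinumab

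*Protocol*

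**What the plan says.** Protocol 12.3.7.3: "The change in each of the laboratory parameters from baseline to each visit will be summarised by visit and treatment group". Protocol 12.3.7.2: "The change in vital signs (blood pressure, heart rate, body temperature) from baseline to each visit will be summarised by visit and treatment group". Each sentence covers the safety, maintenance safety and open-label safety sets together.

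On the reference point, Protocol 7.1 equates baseline with Day 0: "Tralokinumab 600 mg (4 mL) at Day 0 (hereinafter 'baseline'), then 300 mg (2 mL) Q2W". SAP 6.8.1 sets the default: "Unless otherwise specified, the baseline value is defined as the latest pre-dose assessment". Neither document defines a baseline for the open-label period, and SAP 6.7.2 (vital signs) and 6.7.4 (laboratory data) do not change the reference point.

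On who is in the set, Protocol 7.1 says: "Any subject that does not achieve the protocol defined clinical response at Week 16 will be treated with open-label tralokinumab 300 mg Q2W". Protocol 5.6 confirms that this covers both arms: "those who do not achieve a clinical response at Week 16 (including subjects randomised to placebo) will be treated with open-label tralokinumab". Maintenance subjects, including placebo responders, can transfer later, from Week 22. SAP section 5: "The open-label safety analysis set comprises all subjects who at any point in time enter the open-label treatment arm", provided that they receive at least one open-label dose.

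On grouping, SAP 6.8.8 gives the open-label period a single label, "Tralokinumab Q2W + optional TCS". SAP 6.6.5 splits open-label efficacy by initial treatment (Week 16 transfers) or previous maintenance treatment (later transfers), and SAP 6.1 splits baseline characteristics of Week 16 transfers by previous treatment. No such split is stated for laboratory data or vital signs.

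**The concern.** A change reported for open-label tralokinumab should not include change that accrued before the subject had received any tralokinumab. For initial-placebo subjects it does: Day 0 lies at least 16 weeks before first exposure, and that interval may include rescue treatment (Protocol 9.7). For initial-tralokinumab subjects, Day 0 is the last value before tralokinumab. The same column therefore averages two different quantities.

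The plan treats adverse events differently. SAP 6.7.1 assigns an event to a period by its start relative to the first dose of that period, so an event that begins on placebo stays out of the open-label period. A laboratory change that arises in the same weeks is carried into it. Protocol 12.3.7 asks for safety to be presented separately for open-label treatment, and the Day 0 reference weakens that separation.

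At stake is the interpretation of the uncontrolled open-label tables: placebo-period drift, in either direction, could hide or imitate a drug-related change.

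**Working it through.** **Inputs**
- Arm sizes: 585 tralokinumab, 195 placebo (Protocol 12.1).
- Tralokinumab clinical response at Week 16: about 40% (Protocol 7.2).
- Placebo at Week 16: EASI75 15%, IGA 0/1 10% (Protocol 12.1). No rate is given for the combined definition (either one), so it lies between 15% (nested) and 25% (10% + 15%, disjoint).
- Week 52 EASI75 among re-randomised responders: 90%, 55% and 5% on Q2W, Q4W and placebo, with 94, 94 and 47 subjects (Protocol 12.1).
- Dropout before Week 16: no rate given; taken as zero.

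**The plan's own counts.** 780 × 0.75 = 585. 585 × 0.40 = 234, against 235 stated (94 + 94 + 47). These reproduce. The plan does not state the share of the open-label set that first receives tralokinumab there.

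**Share at Week 16**
- Placebo non-responders: 195 × 0.85 = 165.75.
- Tralokinumab non-responders: 585 × 0.60 = 351.
- Share: 165.75 / (165.75 + 351) = 32.1%.
- With 25% placebo response: 146.25 / (146.25 + 351) = 29.4%.

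**Share of the whole set, with later transfers.** As a rough approximation, count every assumed Week 52 EASI75 non-responder as a transfer, and assume that 95% of placebo responders transfer too. The 95% is borrowed from the 5% rate for re-randomised placebo; the actual transfer criteria are different.
- Tralokinumab-arm transfers: 94 × 0.10 + 94 × 0.45 + 47 × 0.95 = 96.35.
- Placebo-arm total: 165.75 + 0.95 × 29.25 = 193.5.
- Share: 193.5 / (193.5 + 351 + 96.35) = 30.2%.

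**Extreme bounds**
- Low: 25% placebo response, no placebo responder transfers, all 234 tralokinumab responders do: 146.25 / (146.25 + 351 + 234) = 20.0%.
- High: every placebo responder transfers and no tralokinumab responder does: 195 / (195 + 351) = 35.7%.

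**What enters the table.** For an initial-placebo subject who transfers at Week 16, change from Day 0 at visit t is (value at t − value at Week 16) + (value at Week 16 − value at Day 0). Only the first term follows exposure. If *w* is the initial-placebo share at that visit, the pooled mean change contains *w* times the mean placebo-period change. Among Week 16 entrants that is about 0.32 times a quantity the documents do not give. At Week 20, the reported change for these subjects covers 16 weeks on placebo and 4 on tralokinumab. For a placebo responder who transfers later, the placebo part is at least 22 weeks.

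**Whether the data for another baseline exist.** Panel 2 schedules vital signs, ECG, chemistry, haematology, IgE and urinalysis at Week 16, and Protocol 10.1 places safety and laboratory assessments before dosing. For later transfers, Panel 3 has vital signs at every visit, chemistry and haematology every 4 weeks, and ECG and urinalysis every 8 weeks up to Week 48, so the latest earlier value is usable where the transfer visit has none.

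**The case against.** The strongest reply is that one Day 0 reference across all periods is a defensible descriptive convention. The drug effect on these parameters is best read from the randomised 16-week comparison of 585 against 195, which summarises the same parameters. Week 16 values by arm appear in the same report, so placebo drift is visible there. The single label does not forbid a split, since open-label efficacy carries it and is split. All of this stands, and it limits the weight of the point. It does not change what the stated rule puts in the open-label tables.

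A second reply is that the SAP default could mean the latest value before the first open-label dose. That reading is not stated, and it would give initial-tralokinumab subjects an on-drug baseline. On either reading the column is mixed and the rule needs a sentence.

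Three stronger inferences are tempting but unsupported:
- *That change from baseline is the only open-label laboratory and vital-sign readout.* Out-of-range values are listed (Protocol 12.3.7.3), the potentially clinically significant limits in SAP 6.7.4 do not depend on baseline, and clinically significant abnormal findings after the first screening visit are reported as adverse events, which are assigned to periods.
- *That a number of placebo-period shifts will be counted against tralokinumab.* The sentence on the shift table names no analysis set, and no rate of leaving the reference range is given.
- *That re-basing alone cures the mixing.* At Week 20 it would compare 20 weeks of tralokinumab with 4. Tralokinumab responders re-randomised to placebo would also keep Day 0, with their maintenance placebo period inside the change.

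**Conclusion.** The point holds as a minor one about interpretation. As written, the rule counts at least 16 weeks of pre-exposure change as open-label change for initial-placebo subjects and pools it with changes from a true pre-tralokinumab value.

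The affected share is about 32% of Week 16 entrants (29% if placebo response is 25%) and about 30% of the whole set, with extreme bounds of 20% to 36%. A reader might take one third as the share of the whole set; that figure fits only the Week 16 entrants. All the shares rest on the planning response rates and no dropout, and the 30% also rests on the transfer approximation above.

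The effect on any mean is that share multiplied by a placebo-period change of unknown size and direction, so no bias can be quantified from the documents. No hypothesis test, alpha allocation or power figure is affected.

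**What to change.** In SAP 6.8.1, add a rule for open-label laboratory and vital-sign change summaries, and for any open-label laboratory or ECG shift table:
- For subjects initially randomised to placebo, baseline is the last available assessment before the first tralokinumab dose: the pre-dose Week 16 value, or for a later transfer the latest scheduled value at or before the transfer visit and before dosing.
- For subjects initially randomised to tralokinumab, baseline stays at Day 0.

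In SAP 6.7.2 to 6.7.4, state that these open-label tables are shown by initial or previous treatment as well as overall, following the split in SAP 6.6.5 for open-label efficacy. The split is needed alongside the new baseline because it separates groups with unequal exposure and isolates tralokinumab responders who were re-randomised to placebo.

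The cost is one derived baseline flag, extra table columns and a footnote explaining two baseline definitions. For some later transfers the baseline value will predate the transfer visit by a few weeks. No new data are needed.
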